5.4. Screen Failures

Consenting to, and screening for the CWMM master protocol and relevant ISAs will occur prior to participants being randomized or assigned to an ISA.

A screen failure occurs when a participant who consents to screening as above but is not subsequently randomized to any ISA or is randomized to an ISA but is not randomized to treatment. A minimal set of screen failure information is required to ensure transparent reporting of screen failures to meet the Consolidated Standards of Reporting Trials (CONSORT) publishing requirements and to respond to queries from regulatory authorities. Minimal information includes demography, screen failure details, eligibility criteria, and any serious adverse event (SAE).

Individuals who are not eligible for participation in this master protocol or are ineligible for relevant ISAs (screen failure) may be rescreened. If a participant does not complete screening procedures within 4 weeks of signing the informed consent forms to confirm eligibility for the master and applicable ISAs, the participant is considered a screen failure. Individuals may rescreen 2 times.

Rescreened participants should be assigned a new participant number. Each time master protocol or ISA rescreening is performed, the individual must sign a new master protocol ICF and ISA ICF(s), as applicable. A screen failure from an ISA who undergoes rescreening under the CWMM master protocol may not require repeating all V401 screening activities if the activities have been completed within 4 weeks of the participant's randomization to a treatment in an ISA. The original laboratory data from the previous participant number will be transferred to the new participant number in instances where this is applicable.

Repeating laboratory tests during the screening period or repeating screening tests to comply with the protocol-designated screening period does not constitute rescreening.

5.5. Criteria for Temporarily Delaying Randomization of a Participant

This section is not applicable to this master protocol. All entry criteria must be met within the specified intervals in the SoA.

A study site could experience a period of time in which no ISA is active at that site. During that time period, screening for the master protocol may continue, but the allowed screening duration of the master protocol, defined in Section 1.3.1 in weeks relative to Week  must still be observed. Participants who have not been assigned to an active ISA before the end of the master protocol screening visit (Visit 401) must undergo rescreening if they wish to continue their study participation.

6. Study Intervention(s) and Concomitant Therapy

Study intervention is defined as any investigational intervention(s), marketed product(s), placebo, or medical device(s) intended to be administered to or used by a study participant according to the study protocol.

6.1. Study Intervention(s) Administered

Study interventions and, if applicable, investigational medical devices are described in the ISAs.

6.2. Preparation, Handling, Storage, and Accountability

See the relevant ISA.

6.3. Measures to Minimize Bias: Randomization and Blinding

Blinding will be maintained throughout the conduct of studies performed under this master protocol. Instances where unblinding may be undertaken are described in the separate Unblinding Plan.

Method of treatment assignment

Assignment to the ISAs and to the treatment groups within the ISAs will be determined by a computer-generated random sequence using an interactive web-response system (IWRS). The randomization ratios are specified in the individual ISAs. ISAs will have randomization ratio details which will depend on anticipated timing of ISA entry, number of active ISAs, required number of participants to be assigned to an active treatment group in the ISA, and desired number of placebo participants to maintain the blind and minimize bias.

Emergency unblinding

Emergency unblinding for AEs may be performed through the IWRS. This option may be used ONLY if the participant's well-being requires knowledge of the participant's treatment assignment. All actions resulting in an unblinding event are recorded and reported by the IWRS.

The investigator has the sole responsibility for determining if unblinding of a participants' intervention assignment is warranted in case of an emergency. Participant safety must always be the first consideration in making such a determination. If the investigator decides that unblinding is warranted, it is the responsibility of the investigator to promptly document the decision and rationale and notify the sponsor as soon as possible.

Discontinuation after unblinding

If an investigator, site staff performing assessments, or participant is unblinded, the participant must be permanently discontinued from study intervention but should continue in the study for efficacy and safety endpoint evaluations and monitoring for all visits.

Additional measures to minimize bias

Additional measures to minimize bias may be described in the ISAs.

6.4. Study Intervention Compliance

This CWMM master protocol section describes compliance for all ISAs. If there are additional ISA-specific measures to assure or assess compliance or adherence, these measures will be described in an individual ISA.

Participant compliance with ISA study interventions should be assessed at each visit.

In addition to the assessment of a participant's compliance with administration of study interventions, other aspects of compliance with the study treatments should be assessed at each visit based on the participant's adherence to the visit schedule, completion of study diaries when applicable, and any other parameters the investigator considers necessary.

Participants considered to be poorly compliant with their study intervention and/or the study procedures will receive additional training and instruction, as required, and will be reminded of the importance of complying with the protocol. Additionally, any specific management of treatment exposures required as a result of poor compliance will be guided by language in the ISAs.

6.5. Dose Modification

Dose modifications, if allowed, are described in the relevant ISA.

6.6. Continued Access to Study Intervention after the End of the Study

Study intervention will not be available at the end of any ISA.

6.7. Treatment of Overdose

See the relevant ISA.

6.8. Prior and Concomitant Therapy

Newly prescribed medications

Investigative site staff will inform participants they must consult with the investigator or a designated site staff member upon being prescribed any new medications during the screening period or following assignment to an ISA. This may not be possible when initiated for treatment of medical emergencies, in which case, the participant will inform the investigator or a designated site staff member as soon as possible.

If the need for additional concomitant medication arises, the participant may be continued in the study and on study intervention if, in the investigator's opinion, the addition of the new medication does not pose a safety risk and the medication is not excluded. If an additional concomitant medication is started, the sponsor should be informed as soon as possible.

Permitted medications

Participants will be permitted to use concomitant medications that they require during the study, except certain medications, for example, other medications for weight management, that may interfere with the assessment of safety and efficacy characteristics of the study treatments.

Doses of other prescription medications for treatment of concurrent medical conditions should remain constant during the study unless an adjustment is medically indicated. For example, doses of antihypertensive medication may be reduced if the participant's BP declines significantly during the study.

Any medication or vaccine (including over the counter or prescription medicines and acetaminophen/paracetamol), vitamins, and/or herbal supplements that the participant is receiving at the time of enrollment or receives during the study must be recorded in the case report form (CRF). Nonsteroidal anti-inflammatory medications (including ibuprofen and aspirin), acetaminophen, cough suppressants, antihistamines, antibiotics, and topical ointments may be used on an as-needed basis without notifying the sponsor and are not restricted by the stable dosing requirements listed earlier.

Prohibited medications

Treatment with, or initiation of, medications that are excluded in the entry criteria (Section 5.2 in this master protocol and, if applicable, in the relevant ISA) may not be used during the study. Some medications required for the management of incident diabetes or incident heart failure (sodium-glucose cotransporter-2 [SGLT2] inhibitors) may be allowed in some ISAs. Specific details may be found in the ISA.

Hormone replacement therapy in postmenopausal females and contraceptives containing an estrogen and a progestin (oral or transdermal system) in premenopausal females should not be started after entering the study. If initiation of such hormonal therapies during the course of the study is deemed necessary by the participant's clinical care team, this may be allowable after consultation with the study medical monitor.

The sponsor should be contacted if a participant starts treatment with a medication that is prohibited by the protocol.

Prescription or over-the-counter medications that are indicated for weight loss are exclusionary if used within 3 months prior to screening or between screening and randomization. These medications are also not allowed at any time during the treatment period. If started after randomization, the medications should be immediately withdrawn. Participants who refuse to withdraw the weight loss medications must be discontinued from study intervention (see Section 7.1).

7. Discontinuation of Study Intervention and Participant Discontinuation/Withdrawal

The following sections describe reasons for

- temporary or permanent discontinuation of a participant's dosing (discontinuation of study intervention), and
- discontinuation (withdrawal) of a participant from the study.

For discontinuation of study sites, of ISAs, or of this master protocol as a whole, see Section [10.1.9](#).

7.1. Discontinuation of Study Intervention

Continuing in the study after discontinuation of study intervention

When necessary, a participant may be **permanently discontinued from study intervention**. If so, the participant should discontinue the study intervention (treatment) and remain in the study and follow select procedures for all remaining study visits, as shown in the SoA of the ISA.

See this master protocol (Section [8](#)) and the relevant ISA (Section 1.3 [SoA] and Section 8) for data to be collected at the time of discontinuation from the study intervention and for activities in the posttreatment follow-up period and for any further evaluations that need to be completed.

Contact the relevant ISA's Lilly-designated medical monitor to determine procedures that may not be necessary for participants who discontinue the study intervention early.

Possible reasons for discontinuation of study intervention

The following reasons for early **permanent** discontinuation of study intervention apply to any ISA conducted under this master protocol.

- Participant decision
 - the participant or the participant's designee, for example, parents or legal guardian, requests to discontinue investigational product.
- Investigator decision
 - the investigator decides that the participant should be discontinued from the study medication.
- If participants answered "yes" to Question 4 or Question 5 on the "Suicidal Ideation" portion of the C-SSRS or answered "yes" to any of the suicide-related behaviors on the Suicidal Behavior portion of the C-SSRS. A psychiatrist or appropriately trained professional may assist in the decision to discontinue the participant.
- If the investigator determines that a systemic hypersensitivity reaction has occurred related to study intervention administration, the participant may be permanently discontinued from the study intervention, and the Lilly-designated medical monitor should be notified. If the investigator is uncertain about whether a systemic

hypersensitivity reaction has occurred and whether discontinuation of study intervention is warranted, the investigator may consult the sponsor.

- Any non-study medication for weight loss is given for more than 1 week, or more than 1 dose of weekly medication.
- Participants will be discontinued from the investigational product in the following circumstances:
 - diagnosis of cirrhosis after randomization
 - diagnosis of an active or untreated malignancy (other than basal or squamous cell skin cancer, in situ carcinomas of the cervix, or in situ prostate cancer) after randomization
 - any treatment-emergent adverse event (TEAE), SAE, or clinically significant laboratory value for which the investigator believes that permanent study drug discontinuation is the appropriate measure to be taken
 - a female participant becomes pregnant, and
 - diagnosis of Type 1 diabetes mellitus or latent autoimmune diabetes in adults.
- If the participant develops any exclusion criterion during the course of the study, the investigator should call the sponsor to determine whether discontinuation of study drug is necessary, and
- Significant noncompliance with the protocol.

7.1.1. Hepatic Criteria for Study Drug Interruption or Discontinuation

Refer to Section [8.2.10](#) for hepatic criteria for study drug interruption or discontinuation.

7.1.2. QTc Stopping Criteria

If a clinically significant finding is identified, including but not limited to changes from baseline in QT interval corrected using Fridericia's formula (QTcF) after enrollment, the investigator or qualified designee will determine if the participant can continue the study intervention and if any change in participant management is needed. This review of the ECG printed at the time of collection must be documented. Any new clinically relevant finding should be reported as an adverse event (AE).

7.1.3. Temporary Interruption of Study Intervention

During the treatment period of an ISA, the investigator may interrupt a participant's study intervention, for example, due to an AE or a clinically significant laboratory value. The dates of study intervention interruption and restart must be documented.

Details regarding temporary discontinuation or interruption and re-introduction of study intervention, if applicable, are described in the ISAs.

7.1.4. Rechallenge

Details regarding restarting study intervention, if applicable, are described in the ISAs.

7.2. Participant Discontinuation/Withdrawal from the Study

Discontinuation is expected to be uncommon.

A participant may withdraw from the master protocol or ISA

- at any time at the participant's own request for any reason or without providing any reason
- at the request of the participant's designee (for example, parents or legal guardian)
- at the discretion of the investigator for safety, behavioral, compliance, or administrative reasons
- if enrolled in any other clinical study involving an investigational product, or enrolled in any other type of medical research judged not to be scientifically or medically compatible with this study, and
- if the participant, for any reason, requires treatment with a therapeutic agent that is prohibited by the protocol and has been demonstrated to be effective for treatment of the study indication. In this case, discontinuation from the study occurs prior to introduction of the new agent.

At the time of discontinuing from the study, if possible, the participant will complete procedures for an early discontinuation visit and posttreatment follow-up, if applicable, as shown in the SoA of the relevant ISA. If the participant has not already discontinued the study intervention, the participant will be permanently discontinued from the study intervention at the time of the decision to discontinue the study.

If the participant withdraws consent for disclosure of future information, the sponsor may retain and continue to use any data collected before such a withdrawal of consent. If a participant withdraws from the study, the participant may request destruction of any samples taken and not tested, and the investigator must document this in the site study records.

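### Section 7.2 takes out of the study a participant who asks before starting an effective weight-loss drug, while 6.8 and 7.1 keep one who starts it and stays on it

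*Protocol*

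**What the plan says.** Three sections of the protocol deal with non-study weight-loss drugs.

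- **6.8, Prior and Concomitant Therapy.** Such drugs are barred throughout the treatment period. "If started after randomization, the medications should be immediately withdrawn". If the participant will not stop, the consequence concerns study drug only: "Participants who refuse to withdraw the weight loss medications must be discontinued from study intervention (see Section 7.1". On newly needed medication in general, 6.8 says "the participant may be continued in the study and on study intervention", provided the medicine is safe in the investigator's view and not excluded. It does not say which of the two ends if the medicine is excluded.
- **7.1, Discontinuation of Study Intervention.** One listed reason for permanently stopping study drug is: "Any non-study medication for weight loss is given for more than 1 week, or more than 1 dose of weekly medication". A participant taken off study drug should "discontinue the study intervention (treatment) and remain in the study and follow select procedures for all remaining study visits".
- **7.2, Participant Discontinuation/Withdrawal from the Study.** The list opens permissively (a participant may withdraw). Its last bullet covers a participant who for any reason needs a prohibited agent known to be effective for the study indication, and ends: "In this case, discontinuation from the study occurs prior to introduction of the new agent". For anyone leaving the study, "if possible, the participant will complete procedures for an early discontinuation visit and posttreatment follow-up, if applicable".

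Section 6.8 points to 7.1 and not to 7.2. The 7.2 bullet points to neither, and nothing sets an order of precedence.

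**The concern.** In an obesity trial, an agent that is both prohibited and effective for the indication is in practice a weight-loss drug. The 7.2 bullet therefore sits next to 6.8 and 7.1, but with the opposite result for follow-up. Under 7.2 the participant leaves the study before the drug is begun; under 6.8 and 7.1 the participant leaves study drug and keeps attending.

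Section 6.8 also tells participants to consult the site when any new medicine is prescribed. The compliant participant is thus the one who meets the 7.2 rule.

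What is at stake is data collection. Section 3 defines the safety estimand without regard to adherence, over the treatment period and safety follow-up. Section 9.3.5 runs all safety analyses on DPS3, which is built the same way. Visits that never took place cannot be restored by any analysis plan.

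**Working it through.** The point is mainly textual, and the plan gives no figure to reproduce.

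**Who falls under which rule**

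1. *Drug already started, then stopped promptly.* 6.8 applies; the participant stays on study drug and in the study.
2. *Drug started and kept.* The refusal clause in 6.8, or the 7.1 limit (more than 1 week, or more than 1 weekly dose), ends study drug, and 7.1 keeps the participant for the remaining visits. Leaving before the drug is introduced is no longer possible, so the 7.2 bullet cannot reach this person.
3. *Need foreseen, drug not yet started.* Neither 6.8's refusal clause nor the 7.1 limit has been triggered. The 7.2 bullet describes this person and states study exit.

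Cases 2 and 3 differ only in whether the participant asked first, yet case 3 leaves the study and case 2 stays.

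**Against the rest of the protocol**

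- 4.1.1 encourages people who stop study drug early to stay for safety monitoring to the end of the treatment period.
- 6.3 stops study drug after unblinding but continues the participant for all visits.

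Both treat stopping study drug and leaving the study as separate matters. The 7.2 bullet joins them.

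**Effect on each data set (9.2) and on disposition (9.3.6.1)**

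- DPS1, used for the primary estimand, ends when study drug stops on either route. At most the cut-off date shifts slightly.
- DPS2 and DPS3 both take treatment-period data regardless of adherence. On the 7.2 route they lose the treatment-period visits after the early discontinuation visit.
- Study-drug discontinuation is recorded on both routes, because 7.2 also stops study drug at exit. Study discontinuation is recorded only under 7.2. Section 9.3.6.1 presents the two separately by treatment group.

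**Illustration of size; every input is an assumption**

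- u = share of an arm who need or use such a drug: 5% (1% to 10%)
- s = share of those who raise it before starting and are exited under 7.2: 50% (25% to 100%)
- f = share of the treatment period still to run: 50% (25% to 75%)

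Early exits per 100 participants = 100 × u × s

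- central: 100 × 0.05 × 0.50 = 2.5
- low: 100 × 0.01 × 0.25 = 0.25
- high: 100 × 0.10 × 1.00 = 10

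Treatment-period person-time lost = u × s × f

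- central: 0.05 × 0.50 × 0.50 = 1.25%
- low: 0.01 × 0.25 × 0.25 = 0.06%
- high: 0.10 × 1.00 × 0.75 = 7.5%

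The high case is a ceiling. It supposes that nobody starts the drug without asking and that every site applies 7.2, and it fits poorly with the protocol's own expectation: "Discontinuation is expected to be uncommon".

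**The case against.** The best defence is that the sections can be reconciled. Section 6.8 is specific, mandatory and names 7.1 as its destination, while 7.2 is a general list that opens with permission. A specific mandatory rule would normally prevail over a general permissive one. The bullet's last sentence can also be read as a timing rule: if someone chooses to leave for this reason, the exit comes first. On that reading nobody is forced out. The reading is available, and it means the text does not clearly compel exit. It does not remove the problem. The sentence is written as a statement of what happens, participant request and investigator discretion already have their own bullets, and an optional reading gives sites no rule for choosing.

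A second defence is that an intervention-specific appendix may settle the matter. It may, and those appendices are not shown. But 7.1 says its reasons apply to every appendix, so the ambiguity recurs until it is settled in the master protocol.

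A third is that little is lost. That is largely right: an early discontinuation visit and posttreatment follow-up are still sought, DPS2 is optional, and no rate of use is given.

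A reader might infer more than this. One could say that 7.2 contradicts 6.8 and 7.1 for everyone who takes a weight-loss drug. The text does not support that, because a participant already on the drug cannot leave before it is introduced, and 6.8 and 7.1 govern that case directly. Nor do the documents show that the safety comparison is biased between arms: nothing states how often such need arises in either arm, so both direction and size are unknown.

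**Conclusion.** The point holds for one group: participants with a foreseen need for an effective, prohibited weight-loss drug who have not yet started it. For them the last bullet of 7.2 states study exit, whereas those who start the drug and stay on it are retained. No stated rationale supports that difference.

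The consequences are missing treatment-period visits in DPS3 and DPS2, and study-discontinuation counts that vary with the section a site follows. The assumed range in the working illustrates scale; it is not an estimate and supports no claim about a between-arm effect. This is a cheap improvement, not a threat to the main result.

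**What to change.** Delete the last bullet of the 7.2 list. Participant request and investigator discretion remain as routes out of the study.

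Alternatively, keep the bullet and replace its final sentence with: *Need for or use of a prohibited weight-loss medication is not by itself a reason to leave the study; it is handled under Sections 6.8 and 7.1, and a participant whose study intervention is permanently discontinued is asked to remain for all remaining visits and Visit 801 unless consent is withdrawn.*

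The replacement should not say that study drug stops as soon as a participant needs or takes such a drug. That would clash with the withdraw-first step in 6.8 and with the tolerance in 7.1 of up to 1 week or 1 weekly dose. No change to 6.8 or 7.1 is required.

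The cost is one edit, with no new visits or assessments beyond those already scheduled. The downside is that some retained safety data will reflect the non-study drug. Section 6.8 requires all medication received during the study to be recorded in the case report form, so those data can be identified.
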